# 5.1.2 Participant Exclusion Criteria

Participants eligible to participate in this trial must **not** meet any of the following exclusion criteria:

1. Have an acute illness, as determined by the site PI or appropriate sub-investigator, within 72 hours prior to study vaccination.

An acute illness which is nearly resolved with only minor residual symptoms remaining is allowable if, in the opinion of the site PI or appropriate sub-investigator, the residual symptoms will not interfere with the ability to assess safety parameters and systemic reactogenicity events as required by the protocol.

2. Have any medical disease or condition that, in the opinion of the site PI or appropriate sub-investigator, is a contraindication to study participation

Including acute, subacute, intermittent, or chronic medical disease or condition that would place the participant at an unacceptable risk of injury, render the participant unable to meet the requirements of the protocol, or may interfere with the evaluation of responses or the participant's successful completion of this trial.

3. Have immunosuppression as a result of an underlying illness or treatment, a recent history or current use of immunosuppressive or immunomodulating disease therapy.

These include oral or parenteral (including intra-articular) corticosteroids of any dose within 30 days prior to study vaccination, or high-dose inhaled corticosteroids within 30 days prior to study vaccination, with high-dose defined as per age as using inhaled high-dose per reference chart in the National Heart, Lung and Blood Institute Guidelines for the Diagnosis and Management of Asthma (EPR-3) or other lists published in UPTODATE. Intranasal corticosteroids are not exclusionary. Low and moderate potency topical corticosteroids are permitted.

- 4. Use of anticancer chemotherapy or radiation therapy (cytotoxic) within 3 years prior to study vaccination.
- 5. Have known active or recently active (12 months) neoplastic disease or a history of any hematologic malignancy. Non-melanoma treated skin cancers are permitted.
- 6. Have known human immunodeficiency virus (HIV), chronic hepatitis B, or hepatitis C infection.
- 7. Have known hypersensitivity or allergy to any components of the study vaccines (AVA, CPG adjuvants, aluminum, benzethonium chloride [phemerol], formaldehyde).
- 8. Have a history of receipt or plan to receive, while enrolled in this study, a licensed or unlicensed anthrax vaccine (except for the vaccines under study herein).
- 9. Have a history of PIMMCs.

Refer to Appendix B: Adverse Events of Special Interest

10. Have a history of alcohol or drug abuse within 5 years prior to study enrollment or test positive on the screening urine test for drugs of abuse.

11. Have any diagnosis, current or past, of schizophrenia, bipolar disease, or other psychiatric diagnosis that may interfere with participant compliance or safety evaluations.

- 12. Have been hospitalized for psychiatric illness, history of suicide attempt, or confinement for danger to self or others within 5 years prior to study vaccination.
- 13. Received or plan to receive a licensed, live vaccine within 30 days before or after each study vaccination.
- 14. Received or plan to receive a licensed, inactivated vaccine within 14 days before or after each study vaccination.
- 15. Have a known history of documented anthrax disease or suspected exposure to anthrax.
- 16. Received immunoglobulin or other blood products, except Rho(D) immunoglobulin, within 90 days prior to study vaccination.
- 17. Received an experimental agent within 30 days prior to the study vaccination or expect to receive another experimental agent during the trial-reporting period.

18. Are participating or plan to participate in another clinical trial with an interventional agent that will be received during the trial-reporting period.

- 19. Female participants who are breastfeeding or plan to breastfeed from the time of the first study vaccination through 30 days after the second study vaccination.
- 20. Planning to donate blood within 4 months following second vaccination.
- 21. Planned elective surgery during study participation.

<sup>10Note that a prospective participant with a positive urine for drugs of abuse test for a medication reported by the participant and used to treat a condition that does not make them otherwise ineligible, may be permitted to enroll, at the discretion of the investigator or his designee.

<sup>11As determined by the site PI or appropriate sub-investigator.

<sup>12Including vaccine, drug, biologic, device, blood product, or medication.

<sup>13Other than from participation in this trial.

<sup>14Approximately 12 months after the second study vaccination.

<sup>15Including licensed or unlicensed vaccine, drug, biologic, device, blood product, or medication.

<sup>16Approximately 12 months after the second study vaccination.

- 22. Member or immediate family member of the site research staff found on the delegation log.
- 23. Previously served in the military any time after 1990 and/or plan to enlist in the military at any time during the study.

#### 5.1.3 Screen Failures

A screen failure is defined as a participant from whom informed consent is obtained and documented in writing, but who is not subsequently randomized to study treatment. Reasons for screen failure are to be recorded on the electronic case report forms (eCRFs).

All screening procedures must occur 2 to 28 days before the Day 1 study visit. On Day 1, participants are allocated to a treatment group and receive their first vaccination. The results of clinical laboratory tests at screening must be within the acceptable ranges for this study. Each clinical laboratory test for screening will not be performed more than twice (one initial and one repeat test for a total of two times). If the laboratory results are abnormal due to a processing or handling error, the test may be repeated without counting towards the not-to-exceed total of twice performed.

Participants who are screen failures are permitted to be rescreened one time (only) according to the PI's discretion. Otherwise eligible prospective participants may undergo additional rescreening visits in the event that they originally failed screening due to an eligibility criterion, such as a laboratory test, that is subsequently amended and does, upon amendment, then allow for inclusion. Such rescreening must occur in the time period before vaccination as specified in the protocol, and a single repeat of any laboratory test, as allowable during the original screening, is again allowable in this situation. In the event that the participant is rescreened for trial participation, a new informed consent form (ICF) must be signed. (This does not apply to those who are simply having an abnormal laboratory test repeated to determine eligibility.) For example, if there are any delays between screening and enrollment that cause eligible participants to fall outside the screening window, these participants may be re-consented and rescreened. Participants who complete the rescreening and are randomized in the study will not be considered screen failures.

## **5.2** Treatment Assignment Procedures

#### **5.2.1** Enrollment and Randomization Procedures

Per ICH E6 GCP, screening records will be kept at the participating VTEU site to document the reason why an individual was screened, but failed trial entry criteria. The reasons why individuals failed screening will be recorded in the Statistical and Data Coordinating Center's (SDCC) Advantage eClinicalSM (Electronic Data Capture System).

Once consented and upon entry of demographic data and confirmation of eligibility for this trial, the participant will be enrolled in the electronic data capture system. The participant will be enrolled and randomly assigned with equal allocation (1:1) to 1 of 2 treatment groups, stratified by age category (18-30 years old and 31-45 years old) and by gender.

Enrollment of participants will be done online using the enrollment module of Advantage eClinicalSM. The randomization code will be prepared by statisticians at the SDCC and included in the enrollment module for this trial. Advantage eClinicalSM will assign each participant to a treatment arm after the demographic and eligibility data have been entered into the system. A designated individual at the VTEU site will be provided with a code list for emergency unblinding purposes, which will be kept in a secure place.

Instructions for use of the enrollment module are included in the Advantage eClinicalSM User's Guide. Manual back-up procedures and instructions are provided for use in the event that the participating VTEU site temporarily loses access to the internet or the online enrollment system is unavailable.

#### **5.2.2 Masking Procedures**

This is a double-blinded (masked) clinical trial.

Participants, site investigators, and study personnel performing any study-related assessments following study vaccine administration are blinded to vaccine received. Laboratory personnel performing immunological assays will receive serum blinded to participant ID number, specimen visit number, and allocation group.

The randomization scheme will be generated by the SDCC and provided to unblinded study personnel (i.e., research pharmacists performing study vaccination preparations and unblinded study vaccine administrators) at the participating VTEU site.

The unblinded study vaccine administrator is a study personnel member credentialed to administer vaccines and may also participate in dose preparation but will not be involved in study-related assessments or have participant contact for data collection following study vaccine administration.

The Safety Monitoring Committee (SMC) may receive data in aggregate and presented by treatment group. The SMC may also be provided with expected and observed rates of the expected AEs in an unblinded fashion and may request the treatment assignment be unblinded for an individual participant if required for safety assessment. The SMC will review grouped and unblinded data in the closed session only.

### 5.2.3 Reasons for Withdrawals and Discontinuation of Study Product Administration

Participants may voluntarily withdraw their consent for trial participation at any time and for any reason, without penalty or loss of benefits to which they are otherwise entitled.

The site PI or appropriate sub-investigator may also withdraw a participant from receiving the study vaccine for any reason.

A participant may withdraw or be withdrawn from this trial for any of the following reasons:

- Medical disease or condition, or any new clinical finding for which continued
  participation, in the opinion of the site PI or appropriate sub-investigator, would
  compromise the safety of the participant, or would interfere with the participant's
  successful completion of this trial, or would interfere with the evaluation of responses.
- Participant withdrawal of consent or refusal to be re-vaccinated.
- Participant loss to follow-up.
- Termination of this trial.
- As deemed necessary by the site PI or appropriate sub-investigator for noncompliance or other reasons.
- New information becomes available that makes further participation unsafe.

### 5.2.4 Handling of Withdrawals and Discontinuation of Study Product Administration

The primary reason for withdrawal from this trial will be recorded on the Study Status electronic Case Report Form (eCRF). Participants will be encouraged to complete the Early Termination Visit. The Early Termination Visit procedures are listed in Section 8.4.

Every attempt will be made to follow all AEs, including solicited injection site and systemic reactions, unsolicited non-serious AEs, SAEs, MAAEs, AESIs (PIMMCs) ongoing at the time of early withdrawal through resolution as per applicable collection times defined for the specific type of AE.

In the case of participants who fail to appear for a follow-up safety assessment, extensive effort (i.e., three documented contact attempts via phone calls made on separate occasions and followed by a certified letter) will be made to locate or recall them, or at least to determine their health status. These efforts will be documented per site protocol.

The site PI or appropriate sub-investigator will inform the participant that already collected data will be retained and analyzed even if the participant withdraws or is withdrawn from this study.

### 5.2.5 Participant Replacement

Participants who withdraw, or are withdrawn or terminated from this trial, or are lost to follow-up after signing the informed consent form (ICF), randomization, and receipt of study vaccine may be replaced. If a participant withdraws after signing the ICF, but before randomization and/or receipt of study vaccine, they may also be replaced. We do not believe that it is likely that there will be any such withdrawals, but, should replacement be required, the total number of persons enrolled may exceed 40 and approval for the overall number enrolled will be obtained from the IRB.

#### **5.2.6** Termination of Study

Although the sponsor has every intention of completing this trial, it reserves the right to terminate this trial at any time for clinical or administrative reasons. Reasons for termination include, but are not limited to, study closure due to SMC review and recommendation, and at the discretion of DMID.

If this trial is prematurely terminated by the sponsor, any regulatory authority, the site PI, or appropriate sub-investigator for any reason, the site PI or appropriate sub-investigator will promptly inform the participants and assure appropriate therapy or follow-up for them, as

necessary. The site PI or appropriate sub-investigator will provide a detailed written explanation of the termination to the IRB.

## 6 STUDY INTERVENTION/INVESTIGATIONAL PRODUCT

## **6.1** Study Product Description

### AV7909 Liquid Formulation

AV7909 (Emergent BioSystems) is an investigational vaccine that is a preformulated, sterile, milky-white suspension (when mixed) for IM injection. It consists of the AVA bulk drug substance and CPG 7909 adjuvant. CPG 7909 is a white to off-white lyophilized powder manufactured by Avecia Nitto Denko (Avecia) in Milford, MA. CPG 7909's natural deoxyribonucleic acid (DNA) phosphodiester backbone has been modified to a phosphorothioate backbone, providing the molecule with increased stability and resistance to degradation for improved in vivo activity. The final base sequence of the full-length CPG 7909 is 24 nucleotides in length.

## AV7909 Lyophilized Formulation

Thermostable AV7909 is a lyophilized version of the liquid AV7909 formulation which, after reconstitution, is a sterile, milky-white suspension for intramuscular injection. The Thermostable AV7909 Bulk Intermediate Product is manufactured at [name] facility by addition of Polysorbate 80 and CPG7909 adjuvant to AVA Bulk Drug Substance produced by Emergent's Manufacturing facility at Lansing, MI.

The Thermostable AV7909 Final Drug Product is manufactured by Integrity Bio Inc. The vaccine is supplied in a 10 mL Schott glass vial with a West 4432/50 Gray stopper treated with FluoroTec® fluorocarbon film and a 20 mm flip-top aluminum seal, stored at 2-8°C. After reconstitution with 4.0 mL Water For Injection, a single vial contains approximately 4.8 mL for a total of 8 doses per vial (0.5 mL each), with ~1.3 mg/mL aluminum, 0.45 mg/mL CPG7909, 0.01% formaldehyde, 22.5 ppm benzethonium chloride (phemerol), 0.025% Polysorbate 80, 0.9% NaCl and 25% trehalose dihydrate at a target pH of 8.0.

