**Estimated Time to Complete** 

**Enrollment:** 

Approximately6 months

**Description of Agents:** • AV7909 liquid formulation vaccine

• AV7909 lyophilized formulation vaccine

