# Description of Study Design:

The study is a phase I randomized, parallel-group, double-blind controlled interventional trial in which the safety, tolerability, and immunogenicity of 2 formulations of adjuvanted anthrax vaccine (AV7909), lyophilized and liquid, both manufactured by Emergent BioSolutions, will be assessed and compared. AV7909 is an investigational vaccine that combines the currently licensed Anthrax Vaccine Adsorbed (AVA, BioThrax) with the adjuvant CPG 7909, an oligonucleotide. Forty healthy young adults, 18 to 45 years old, inclusive, who meet all eligibility criteria, will be randomly allocated to one of two study groups in a 1:1 ratio: 20 will receive AV7909 as the thermostable lyophilized product and 20 will receive AV7909 as the liquid product. Stratification by age category and by gender will assure that near equal numbers of younger (18-30 years) and older (31-45 years) males and females are assigned to each vaccine. The vaccines will be given intramuscularly in a 2-dose schedule, 2 weeks apart. Data entry will be "direct", that is, without the significant use of paper source documents or case report forms. Participants will be followed for safety and tolerability by in-person visits, electronic reactogenicity records (eMemory Aids), and safety laboratory values. A Safety Monitoring Committee will evaluate the safety data if halting rules are met or if deemed necessary by the sponsor or principal investigator. Immunogenicity will be evaluated by prevaccination and multiple post-vaccination assessments of toxin-neutralizing antibodies and IgG anti-PA antibodies assayed by Enzyme Linked ImmunoSorbent Assay (ELISA) over approximately one year. Participants will be followed for 1 year following the second dose of vaccine.

Safety will be assessed by evaluation of laboratory values, non-serious unsolicited Adverse Events, Serious Adverse Events (SAEs), Medically Attended Adverse Events (MAAEs), and Adverse Events of Special Interest (AESIs), which, for this protocol, are defined as Potentially Immune-Mediated Medical Conditions (PIMMCs). Unsolicited non-serious adverse events (AEs) will be collected from Day 1 through approximately Day 64, inclusive. SAEs, MAAEs, and AESIs (PIMMCs) will be collected from the time of study vaccination through approximately Day 380. Clinical safety laboratory evaluations will be performed at screening and at approximately Day 29

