#### 2.2 Scientific Rationale

The anthrax vaccine that is currently licensed in the US, AVA, has been shown to be safe and immunogenic in people and has been shown to lead to antibody responses that, in non-human primate models of lethal anthrax spore challenge, are protective, even in the absence of

antibiotics. However, the vaccine was first given subcutaneously, leading to significant local reactogenicity, and it requires 3 priming doses and an onerous schedule for recipients to remain immune. An improved vaccine that leads to faster immune responses and requires fewer doses, while remaining safe and well tolerated, would be welcomed.

Due to the large number of doses required to generate a primary immune response in humans that leads to putative protective levels, as evidenced by animal challenge model protection, various approaches have been taken to improve anthrax vaccines. One approach that has proven successful to date is the addition of the TLR9 agonist adjuvant CPG 7909 to the currently licensed vaccine. This new vaccine, named AV7909, is being developed by Emergent BioSolutions as a vaccine with an indication for postexposure prophylaxis (PEP) that is intended to decrease the risk of anthrax disease after exposure. AV7909 has been shown to be safe and has improved immunogenicity when compared to AVA. Early studies have shown that the addition of CPG 7909 to AVA has allowed for intramuscular injection, a priming series of only 2 doses, and resulted in more rapid induction of putatively protective antibody responses. AV7909 has been studied in animals and humans with a safety record similar to AVA itself. This vaccine, once studied in increasing numbers of persons, may prove superior enough to AVA to allow it to replace AVA as the standard of care. However, the current formulation is liquid and therefore prone to a shorter shelf life and stricter temperature storage requirements. Since anthrax vaccine sufficient for a response to an intentional act of bioterror is stored in the National Strategic Stockpile, a thermostable (lyophilized) formulation of the AV7909 adjuvanted anthrax vaccine would offer many advantages to a liquid formulation.

The proposed trial will assess, in healthy adults, the safety, reactogenicity, and immunogenicity of the thermostable lyophilized formulation of AV7909 compared to the liquid formation of AV7909.

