Vaccine Administration Risks. The risk profile for AVA (BioThrax) is well known, given that millions of persons have been vaccinated. The risks of AV7909 are less well characterized, given that fewer persons have been vaccinated with this product.

Risks of AVA (BioThrax). Since the licensure of BioThrax in 1970, more than 3.3 million individuals, primarily military personnel, have been vaccinated in the pre-exposure setting. The safety profile of BioThrax and its associated risks are summarized in the BioThrax prescribing information. The most common ( $\geq 10\%$ ) local (injection-site) adverse reactions observed in clinical studies are tenderness, pain, erythema, edema, and arm motion limitation. The most common ( $\geq 5\%$ ) systemic adverse reactions are muscle aches, headache, and fatigue.

Risks of CPG 7909. CPG 7909 has been investigated clinically since the mid-1990s for indications that have included cancer monotherapy, combination use with anti-cancer therapies, and vaccine adjuvant against infectious diseases and cancers. Potential risks associated with AV7909 include hypersensitivity reactions, autoimmune reactions, and more minor local and systemic reactogenicity effects. Other oligonucleotides have been evaluated as vaccine adjuvants, including CPG1018, the adjuvant in Heplisav-B, a hepatitis B vaccine now licensed in the US for persons 18 years and older.

Risks of AV7909. Emergent BioSolutions has sponsored three completed clinical studies in healthy participants 18 through 50 years of age as part of the AV7909 development program: a phase 1, a phase 1/2, and a phase 2 trial.  A total of 241 participants have been exposed to a

combination of AVA and CPG7909. In the initial trial, a formulation with AVA + 1.0 mg CPG 7909 was tested and was well tolerated with a trend toward increased frequency and severity of local and systemic reactions in the AV7909 formulation compared to BioThrax. The second trial identified a formulation of AV7909 with a lower CPG7909 concentration (0.25 mg CPG 7909) for further clinical development that produced an enhanced immune response without increased reactogenicity. This formulation was evaluated in the phase 2 trial described below and is the formulation to be tested in the current study.

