In 2014, a phase 2, randomized, double-blinded, BioThrax-controlled study was conducted to evaluate the safety and immunogenicity of 3 IM vaccination schedules and 2 dose levels of AV7909 in 168 healthy adults.  The results of this study found that AV7909 was well tolerated: 4.2% of subjects discontinued vaccination due to AEs; no serious adverse events (SAEs) were reported that were potentially vaccine related; no reported AEs of potential autoimmune etiology were reported. The vaccine produced a more rapid immune response compared to BioThrax as measured by TNA NF50 values≥0.56 (a putative correlate of protection) obtained through Day 63.

Hypersensitivity and Anaphylactic/Anaphylactoid Reactions. Parenteral administration of any protein product may be associated with immediate-type hypersensitivity reactions that can manifest as urticaria, shortness of breath, wheezing, nausea and cramping, and in severe cases, hypotension. Acute allergic reactions, including anaphylaxis, have occurred with BioThrax. Reports of hypersensitivity, urticaria, and pruritus have rarely occurred following administration of AV7909. Appropriate medical treatment and supervision will be available to manage possible anaphylactic reactions following administration of the vaccine and the vaccine will not be administered to participants with known sensitivity to any of the vaccine components, e.g., synthetic oligodeoxynucleotides (ODNs), formaldehyde, benzethonium chloride (phemerol), or aluminum. The vaccine stoppers do not contain latex.

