Pregnancy and Lactation. No reproductive toxicity studies have been performed with AV7909. BioThrax can cause fetal harm when administered to a pregnant woman. CPG 7909 has been

determined to be embryolethal in rabbits and teratogenic in developing rats and rabbits at doses far in excess of the individual vaccination dose for AV7909 (0.25 mg). In rats, fetal skeletal anomalies were noted when administered at a dose of > 3 mg/kg/day; in rabbits, slightly reduced numbers of viable fetuses were noted when administered at a dose of 3 mg/kg/day, and external, visceral, and skeletal malformations occurred when administered at >1 mg/kg/day.

Given these findings, breastfeeding or a positive pregnancy test will preclude study enrollment. All women of childbearing potential will have a negative pregnancy test before each vaccine administration and will agree to use effective contraception from at least one month prior to Day 1 and continued through Day 75 (60 days after second vaccination). Confirmed pregnancy will result in discontinuation of vaccinations. Participants who become inadvertently pregnant during the trial will be monitored for pregnancy outcomes, if the participant provides permission, according to protocol-specified procedures.

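### Do the protocol's two CPG 7909 figures (0.25 mg stated, 0.225 mg implied for a lyophilized dose) call for a change to the plan?

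*Protocol*

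**What the plan says.** The only CPG 7909 figure tied to the lyophilized product is in Protocol Section 6.1, AV7909 Lyophilized Formulation. After reconstitution with 4.0 mL of water the vial holds about 4.8 mL, for "8 doses per vial (0.5 mL each), with ~1.3 mg/mL aluminum, 0.45 mg/mL CPG7909". Section 6.1.1 repeats the 0.5 mL dose volume for this product and gives the same volume for the liquid. Neither section gives a CPG 7909 concentration for the liquid.

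The 0.25 mg figure appears twice in Section 2.3.1, Potential Risks:

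- Under Risks of AV7909, the second of three completed trials "identified a formulation of AV7909 with a lower CPG7909 concentration (0.25 mg CPG 7909" in milligrams, with no volume). The text adds that this formulation went into the phase 2 trial and "is the formulation to be tested in the current study".
- Under Pregnancy and Lactation, animal toxicity doses are set against the "individual vaccination dose for AV7909 (0.25 mg").

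The phase 2 trial itself covered "3 IM vaccination schedules and 2 dose levels of AV7909 in 168 healthy adults", so the clearest per-vaccination reading of 0.25 mg comes from the pregnancy paragraph.

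Naming is not uniform. The Protocol Summary says the trial assesses "2 formulations of adjuvanted anthrax vaccine (AV7909), lyophilized and liquid", and its list of agents includes the "AV7909 lyophilized formulation vaccine", so both products carry the AV7909 name. The study title and Section 6.1, on the other hand, call the lyophilized product Thermostable AV7909. Section 2.2 says: "However, the current formulation is liquid and therefore prone to a shorter shelf life". SAP Section 4.4.2 sends the reader to the protocol for formulation details.

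**The concern.** A reader who multiplies concentration by volume gets 0.225 mg for a lyophilized dose, then finds 0.25 mg stated for AV7909 and for the formulation to be tested here, with no exception for either arm. Section 2.3.1 also speaks of one formulation under test, although the trial tests two.

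That suggests two possibilities: one of the figures is mistaken, or the arms differ in adjuvant content and the protocol does not say so. The second would bear on interpretation. CPG 7909 is the component that Section 2.2 credits with the faster response, and the secondary objective is an initial comparison of immunogenicity between liquid and lyophilized vaccine. If adjuvant content differed, a difference in titers or reactogenicity could not be put down to lyophilization alone.

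**Working it through.** **Inputs.** CPG 7909 at 0.45 mg/mL, dose volume 0.5 mL, diluent 4.0 mL, vial volume about 4.8 mL, 8 doses per vial (Protocol Section 6.1; dose volume also in 6.1.1). Stated amount 0.25 mg (Section 2.3.1).

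**1. Amount per lyophilized dose.** Concentration × volume = 0.45 × 0.5 = 0.225 mg. The difference is 0.25 − 0.225 = 0.025 mg, and 0.225 / 0.25 = 0.90, so the implied amount is 10% lower. Over two doses the totals are 0.45 mg and 0.50 mg.

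**2. Can rounding explain it?** A printed 0.45 mg/mL covers 0.445 to 0.455, giving 0.2225 to 0.2275 mg. A printed 0.25 mg covers 0.245 to 0.255 mg. The ranges do not overlap. The gap runs from 1 − 0.2275/0.245 = 7.1% to 1 − 0.2225/0.255 = 12.7%. The approximation sign in Section 6.1 stands before the aluminum figure, not the CPG 7909 figure.

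**3. Can a different volume explain it?**

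| Reading of Section 6.1 | Volume per dose | CPG 7909 |
|---|---|---|
| Stated dose volume | 0.5 mL | 0.225 mg |
| Diluent volume over 8 doses (4.0 / 8) | 0.5 mL | 0.225 mg |
| Vial volume over 8 doses (4.8 / 8) | 0.6 mL | 0.27 mg |
| Volume needed for 0.25 mg (0.25 / 0.45) | 0.556 mL | 0.25 mg |

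The protocol states 0.556 mL nowhere. At 0.5 mL, 0.25 mg would need 0.50 mg/mL. The stated 0.25 mg cannot be reproduced from Section 6.1.

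**4. Do the two figures describe the same product?** Section 6.1 is explicit: the lyophilized product after reconstitution. Section 2.3.1 is not. Its 0.25 mg belongs to the formulation studied in completed AV7909 trials. On composition that is hard to read as the lyophilized product: Section 6.1 describes the liquid as AVA bulk substance plus CPG 7909, while the lyophilized product adds Polysorbate 80 and lists 25% trehalose dihydrate. With Section 2.2 calling the current formulation liquid, a liquid-only reading is natural. On that reading 0.25 mg and 0.225 mg describe different products and do not conflict, though the sentence about the formulation under test lacks a qualifier.

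**5. Does anything in the plan use the figure?**

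- Dosing is by volume, 0.5 mL in both arms (Section 6.1.1). The milligram figure does not enter what is drawn up.
- The SAP summarizes titers, concentrations, response proportions and adverse events by arm. None of its analyses uses CPG 7909 content.
- The sample-size tables (Protocol 11.4.3, SAP Section 5) rest on event frequencies and response proportions.
- In the pregnancy paragraph 0.25 mg serves only as a yardstick for animal doses of about 1 to 3 mg/kg/day, described there as far larger. Using 0.225 mg would widen any such margin by a factor of 0.25 / 0.225 = 1.11 and leave the statement intact.

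**The case for a change.** The strongest opposing case is that the liquid-only reading has to be supplied by the reader. Neither statement in Section 2.3.1 limits itself to one arm, the Protocol Summary uses AV7909 for both products, and Section 6.1 calls the lyophilized product a version of the liquid one without mentioning a change in adjuvant content. Nor can the reader settle the matter within the protocol, because no CPG 7909 concentration is given for the liquid. SAP Section 4.4.2 points to the protocol, not to the Investigator Brochures. So either a figure is off or a sentence is too broad, and on both accounts some text needs attention.

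Most of this stands. The arithmetic is right, the gap is outside rounding, and the scope of the 0.25 mg statements is unclear. Section 6.1.1 refers to the Investigator Brochures for both vaccines, which may hold the liquid figure but are not available here.

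What does not stand is the step from unclear wording to a fault in the comparison. The trial sets one whole product against another (Protocol Section 4, SAP Section 2.1), and the two already differ in excipients on the protocol's own description. Any difference in CPG 7909 content would be part of the product difference under assessment. Section 11.2 adds that no formal null hypothesis is tested. The contrast remains randomized and interpretable as liquid product versus lyophilized product; attributing it to lyophilization alone is a claim the plan does not depend on.

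**Conclusion.** No change to the plan is called for. The discrepancy in the text is real: 0.225 mg implied against 0.25 mg stated, a gap of 0.025 mg or 10% (7.1% to 12.7% with rounding of both figures). It is an ambiguity of scope in background wording. The documents do not establish that a figure is wrong or that the arms differ in adjuvant content.

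This rests on three points that can be checked in the documents: both arms are dosed at 0.5 mL by volume, no planned analysis or sample-size calculation uses milligrams of CPG 7909, and the comparison is between whole products. It also rests on one assumption, that the 0.25 mg statements may refer to the liquid, which is plausible but not stated. If that assumption fails, one figure needs correcting, but randomization, endpoints, sample size and analyses are still unaffected.

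Section 6.1 and the two statements in Section 2.3.1 should be reconciled against the product specification, so that the text says which product the 0.25 mg describes. That is a clerical matter, and nothing here implies which figure is right. If the specification shows that adjuvant content does differ, the study report can describe the comparison accordingly without any change to the SAP.
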